The groups will be allocated at random and thus the distribution of the data should be similar. A student's t-test will be used to compare the two groups for the primary and secondary end points. Descriptive statistics (proportions, mean, medians, standard errors and ranges) will be computed for all baseline variables with 95% CI using either exact binomial confidence intervals or t-confidence intervals for continuous outcomes (after appropriate transformation of the outcome to symmetry). All tests will be conducted at alpha=0.05. Previous studies investigating the effects of obesity surgery on macronutrient intake have recruited 50 patients per group and had power to detect significant differences. This type of study has never been performed with incretin pharmacotherapies and therefore will serve as a pilot for the investigation of the effects of this treatment intervention. The standardised meal study will have 80% statistical power to detect a difference of 5 pmol/L from the expected mean PYY level of 30 pmol/L when the usual standard deviation is 8 pmol/L, the sample size 20 subjects and the alpha error level 5%. This power calculation has been based on previous published results by the same group. Therefore 20 patients in each group are needed.

For the metabolic study, the endpoint is the minimum endogenous glucose production rate. Based on the HOMA-IR results from the only published study on patients having undergone the Endobarrier procedure, we will have a power of 81% at a p level of <0.05 if 6 patients complete the study. To allow for patients dropping out, a maximum of 10 patients will be enrolled to ensure 6 patients complete the study.

8. Regulatory Issues

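### The 80% power quoted for PYY is a one-sample figure; the two-group t-test that the plan names has about 49% power with 20 patients per group

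*Combined protocol and SAP*

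**What the plan says.** Section 7 (Statistics and Data Analysis) names one inferential test: "A student's t-test will be used to compare the two groups for the primary and secondary end points". All tests are at alpha 0.05; sidedness is not stated. Section 3.1 lists gut hormones among the secondary outcomes, so this test applies to PYY.

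The sample size for the meal study is then justified by a claim of "80% statistical power to detect a difference of 5 pmol/L from the expected mean PYY level of 30 pmol/L". The inputs given for this are an SD of 8 pmol/L, described only as the usual one, 20 subjects and a 5% alpha error. The conclusion drawn is: "Therefore 20 patients in each group are needed". Section 3 (Study Design) accordingly enters 20 patients from each of the eight groups into the meal tests.

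**The concern.** The wording of the power statement describes one group of 20 measured against a known reference value. The test named in the same section compares two groups, and both means are then estimated with error. The variance of a difference between two independent means of 20 is twice that of a single mean of 20, so inputs that give 80% power in the first setting cannot do so in the second.

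This is the only calculation that supports 20 per group in the meal study, where each patient attends five meal tests with eight blood samples at each. If the true power between groups is near one half, a non-significant PYY comparison says little. A reader relying on the stated 80% could take it as evidence that the interventions do not differ.

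**Working it through.** **Inputs, all from Section 7:** difference 5 pmol/L; SD 8 pmol/L; n = 20 (per group, by the plan's own conclusion); alpha 0.05. Two-sided testing is assumed, and one-sided is shown as a check. The standardised difference is 5/8 = 0.625. The t-test powers use the noncentral t distribution.

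**Step 1. Reproduce the stated 80%.** One sample against a fixed mean, SD treated as known:

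- Power = Φ(5·√20/8 − 1.96) = Φ(2.795 − 1.96) = Φ(0.835) = 79.8%.
- Required n = [8 × (1.96 + 0.8416)/5]² = 20.1.

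Both the 80% and the 20 are recovered, so this is very probably the calculation that was done.

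**Step 2. The same one-sample design, analysed by t-test.** Noncentrality 2.795 on 19 df gives 75.5%. The difference detectable with 80% power is 5.3 pmol/L. A paired pre/post t-test gives the same result if 8 is the SD of the change.

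**Step 3. The test the plan names.** Two groups of 20:

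- Standard error of the difference = 8·√(2/20) = 2.530.
- Noncentrality = 5/2.530 = 1.976 on 38 df; the two-sided critical value is 2.024.
- Power = 48.7% (normal approximation 50.7%), so the type II risk is 51%, not 20%.
- Difference detectable with 80% power at 20 per group: 7.3 pmol/L.
- Patients per group for 80% power at 5 pmol/L: 42 (41 gives 79.8%).

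**Step 4. Other readings of the plan.**

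| Reading | Power |
|---|---|
| Two-group t-test, 20 vs 20, one-sided | 61.6% |
| One-sample t-test, one-sided | 85.3% |
| 20 vs both control groups pooled (20 vs 40), two-sided t | 61.2% |
| 20 patients in total (10 vs 10), two-sided t | 26.3% |

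None gives 80%, and the plan does not mention pooling.

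**Step 5. Within-patient reading with 8 as the between-patient SD.** The SD of the change is 8·√(2(1 − r)), where r is the pre/post correlation. The documents give no value of r, so the following are assumptions:

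| Assumed r | SD of change (pmol/L) | Paired t-test power, n = 20 |
|---|---|---|
| 0 | 11.3 | 46.7% |
| 0.3 | 9.5 | 61.1% |
| 0.5 | 8.0 | 75.5% |
| 0.6 | 7.2 | 84.2% |
| 0.7 | 6.2 | 92.8% |

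Dropout and multiple comparisons are not allowed for in any of these figures; either would lower them.

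**The case against.** The strongest reply is that the 80% was never meant as a between-group figure. It speaks of "a difference of 5 pmol/L from the expected mean PYY level of 30 pmol/L" and of a single sample size of 20, which is one-group language, and as such the sum is nearly right. Each patient has one meal test before and four after the intervention, so a pre/post test within each group is a natural analysis, and 20 in each group could mean 20 for each group's own test. Step 5 shows that such a test would exceed 80% at an assumed correlation of 0.6 or more. The sentence naming the t-test is also a poor anchor: it speaks of two randomly allocated groups, whereas Section 3 describes an observational study with eight. Finally, PYY is one analyte within a secondary outcome, and the source of the SD is not visible.

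Part of this stands. The within-patient reading is plausible, and the 49% is conditional on a two-sided between-group test with a between-patient SD of 8. But Section 7 names no paired test for PYY and describes 8 only as the usual SD, not as the SD of a change. The sentence in Section 3 that makes pre/post comparison the basis of analysis concerns energy and macronutrient intake, not gut hormones. Even on the most favourable reading of 8, the t-test has 75.5%, and whether a paired test reaches 80% depends on a correlation that the plan does not give. The ill-fitting test sentence is a further reason to state the comparison, not a reason to leave the 80% in place.

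**Conclusion.** The concern holds. The stated power does not belong to the test the plan names. For that test, with 20 per group, a difference of 5 pmol/L, SD 8 and two-sided 5% alpha, power is 48.7% instead of 80%, and 80% power applies to a difference of about 7.3 pmol/L instead of 5. One-sided testing would give 61.6%, which does not close the gap. If a pre/post comparison within each group is intended, the figure is 75.5% when 8 is the SD of change; otherwise it cannot be fixed from the documents. The primary endpoint and its 50 per group are not affected.

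**What to change.** Keep 20 per group and correct the statement in Section 7.

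- **If the comparison is between groups:** state about 49% power for 5 pmol/L and 80% power for 7.3 pmol/L (two-sided 5%, SD 8), and name the pair or pairs of groups compared.
- **If it is within patients:** say so, name the paired test and the time points, and give the SD of the change with its source. If that SD is 8, state 76% power for 5 pmol/L and 80% for 5.3 pmol/L.

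In either case, say whether 8 pmol/L is a between-patient SD or an SD of change, and state the sidedness.

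As an option for the between-group analysis, adjust PYY for the pre-intervention meal-test value by ANCOVA. With residual SD 8·√(1 − r²), two-group power would be 52%, 60%, 77% or 83% for assumed correlations of 0.3, 0.5, 0.7 or 0.75. These figures also assume similar baseline means, which groups formed by planned treatment do not guarantee, so they should not replace the unadjusted figure as the headline.

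The cost is a change of wording and a less favourable stated power. No patients or visits are added; the baseline meal test is already scheduled.

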
20 patients in each group will undergo more detailed measurements of food intake, hunger, satiety, gut hormones and bile acids. The research protocol will be the similar to that previously published by the Department of Metabolic Medicine, Imperial College, London. Participants will be fasted for 12 hours overnight and will attend for the study on 5 occasions. On each occasion venous blood samples will be taken and visual analogue scores will be measured over a 3 hour period using previously published methodology (Appendix Table 1: Test Periods). Samples or sample containers will be anonymised before collection but will be traceable back to the individual patients. Urine will be collected once. A qualified medical doctor will insert a venepuncture cannula into the arm of the patient and 5ml blood will be withdrawn at baseline, 15, 30, 60, 90, 120, 150 and 180 minutes following ingestion of a

standard 400kcal meal as below (Appendix Table 2: Protocol of each Test). After each sample the cannula will be flushed with saline to keep it patent. The protocol will be carried out 5 times per patient, pre intervention, 2, 7-30 days, 3 and 6-12 months post intervention. Plasma samples will be analysed for gut hormones as well as for primary bile acids and lipids. An extra blood and urine test will be obtained 1 month after treatment but not followed by a meal test.

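### The meal study puts through exactly the 20 patients per group that its 80% power needs, with no allowance for dropout over five visits, so the stated power has no reserve

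*Combined protocol and SAP*

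**What the plan says.** The power statement is in Section 7 (Statistics and Data Analysis): "The standardised meal study will have 80% statistical power to detect a difference of 5 pmol/L". The difference is measured against an expected mean PYY of 30 pmol/L, "when the usual standard deviation is 8 pmol/L", with 20 subjects and a 5% alpha. The conclusion drawn is "Therefore 20 patients in each group are needed".

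Section 3 (Study Design) uses the same number for the patients who are tested: "20 patients in each group will undergo more detailed measurements of food intake, hunger, satiety, gut hormones and bile acids". On the schedule it says: "The protocol will be carried out 5 times per patient, pre intervention, 2, 7-30 days, 3 and 6-12 months post intervention". Each visit follows an overnight fast and includes three hours of cannula sampling. Section 6 puts the last meal test at 12 months, whereas Section 3 and Appendix Table 1 say 6-12 months. Those passages need reconciling, but the point here is the same on either reading.

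For the clamp (metabolic) study, the next paragraph of Section 7 does provide for loss: "To allow for patients dropping out, a maximum of 10 patients will be enrolled to ensure 6 patients complete the study".

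Section 8.2 lets participants withdraw at any time. No dropout allowance, replacement rule or method for missing visits is given for the meal study.

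**The concern.** The number the calculation needs and the number put through the tests are both 20. The calculation counts patients with a usable PYY value. A five-visit schedule lasting up to a year will keep all 20 in every group only if nobody withdraws or misses a visit. Section 7 recognises this for one sub-study and is silent on it for the other.

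What is at stake is how the late visits are read. Lasting changes in gut hormones and bile acids will be judged there, and losses will have accumulated by then. A null result at that point could be reported as coming from an 80%-powered comparison when fewer than 20 patients per group contributed.

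**Working it through.** **Inputs (Section 7).** Difference 5 pmol/L, SD 8 pmol/L, n = 20, alpha 5%. Whether the test is one- or two-sided is not stated; two-sided is used here.

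**Step 1: reproduce the plan's figure.** The wording, "a difference of 5 pmol/L from the expected mean PYY level of 30 pmol/L", describes a one-sample comparison. With the normal approximation:

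power = Φ(5√n / 8 − 1.960)

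At n = 20: 5 × 4.472 / 8 = 2.795; 2.795 − 1.960 = 0.835; Φ(0.835) = 79.8%.

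Solving for n at 80% power: (8 × (1.960 + 0.842) / 5)² = 20.09.

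The stated 80% is reproduced. The other versions at n = 20 do not give it: one-sample t, two-sided, 75.5%; one-sample normal, one-sided, 87.5%; one-sample t, one-sided, 85.3%; two-sample normal, two-sided, 50.7%; two-sample t, two-sided, 48.7%. Since 20.09 patients are needed and 20 are tested, there is no reserve.

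**Step 2: let some of the 20 be lost.** The documents give no loss rate for the meal study. The range of 10-40% is an assumption. The two-group column uses the noncentral t with noncentrality 5 / (8√(2/n)) and 2n − 2 degrees of freedom, because Section 7 plans a Student's t-test between two groups. Its noncentrality at n = 20 is 5 / (8 × 0.3162) = 1.976.

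| Assumed loss | Completers per group | One-sample normal (plan's basis) | One-sample t | Two-group t-test (planned test) |
|---|---|---|---|---|
| 0% | 20 | 79.8% | 75.5% | 48.7% |
| 10% | 18 | 75.5% | 70.5% | 44.5% |
| 20% | 16 | 70.5% | 64.7% | 40.2% |
| 30% | 14 | 64.7% | 58.1% | 35.7% |
| 40% | 12 | 58.1% | 50.6% | 31.0% |

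**Step 3: entrants needed to finish with 20.** Using 20 / (1 − loss), rounded up: 23 at 10%, 25 at 20%, 29 at 30%, 34 at 40%.

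**Step 4: is there room within 50 per group?** Section 3 requires the clamp patients to be different people and gives ten to twenty per group. That leaves 50 − 20 = 30 to 50 − 10 = 40 places for the meal study.

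- Up to 30% loss, 29 entrants fit even with 20 clamp patients (29 + 20 = 49).
- At 40% loss, 34 entrants fit with 10 clamp patients (44) but not with 20 (54).

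**Step 5: the clamp comparison.** Ten enrolled for six completers is a margin of 1 − 6/10 = 40%.

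**The case against.** - **The clamp margin is not a forecast.** A reader might infer that the plan itself expects 40% dropout and that 58.1% is therefore its own implied meal-study power. The text does not support this. Section 7 sets a maximum enrolment so that six will complete, which is a safety margin. Section 3 also gives a different clamp number (ten to twenty per group), so the ratio is not fixed across the document. Clamp visits are heavier too, with two cannulas, insulin and tracer infusions, up to seven hours and a liquid diet. The 40% row is only the top of an assumed range. What stands is the narrower contrast: one sub-study has an allowance and the other has none.
- **Loss may be small where it matters.** The visit to which the PYY power refers is not named. By day 2 or days 7-30 few patients may have left. This is correct, and it makes the shortfall conditional on loss at the visit in question.
- **Twenty may mean completers.** Section 3 says that 20 will undergo the tests; it does not say that 20 will be enrolled. That reading is possible, but the number to be entered would then be stated nowhere.
- **The mismatch with the planned test is larger.** This is also true. With 20 per group the two-group t-test has about 49% power before any loss, and 80% would take 42 per group. Restating only the one-sample figures would leave the plan overstated, so the remedy has to cover both.
- **The dietary study.** A reader might extend the point to the 50 per group recruited for diet. Section 7 claims no 80% power there, and it cites earlier studies by the number they recruited, which may already include their losses. The point is not made for diet.

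**Conclusion.** The point holds as an omission; the plan's arithmetic is not wrong on its own basis. The stated 80% needs all 20 patients per group to be evaluable, and nothing in the plan protects that number. On the plan's own basis, losing two patients per group costs about 4 percentage points (79.8% to 75.5%), losing four about 9 (to 70.5%) and losing eight about 22 (to 58.1%).

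The direction is certain for any loss. The size rests on an assumed loss rate and on which visit the calculation concerns. It would be wrong to say flatly that the stated power will not be delivered because of dropout: at an early visit with complete attendance, the plan's one-sample figure is unaffected.

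The one-sample figures apply only if a within-group comparison is intended, and then only if 8 pmol/L is the SD relevant to that comparison (for a paired analysis, the SD of the change). For the two-group test that Section 7 describes, power runs from about 49% with no loss to 31% with 12 per group.

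The change should be made: it is cheap, and it affects how late null results are read.

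**What to change.** In Section 7:

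1. State a dropout assumption for the meal study, with its basis.
2. Name the visit to which the PYY power refers.
3. Restate power at the expected number of completers for the test actually planned. For the two-group t-test that is about 49% at 20, 45% at 18, 40% at 16 and 31% at 12 per group. If a within-group comparison is what is meant, say so, confirm which SD the 8 pmol/L is, and give the one-sample or paired figures instead.
4. Optionally, add a replacement rule: a later recruit to the same group, not yet treated and not in the clamp study, may take the place of a meal-study dropout. The rule should be limited to the places left within the 50 per group. It cannot be relied on to restore 20 completers in every case, since 34 meal-study and 20 clamp patients would exceed 50. Late losses are also harder to replace, because the new patient must still complete the full schedule.

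The cost is a few sentences and power figures that look less favourable. The total of 400 does not change.

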Patient will attend the investigation unit after an overnight fast. They will be weighed and an intravenous cannula will be inserted in the antecubital of each arm. The first cannula will be used for infusions and the other for blood sampling. Participants will be asked to provide a urine sample that will be tested for albumin creatinine ratio and metabolic/inflammatory markers. If blood glucose levels are high on arrival an insulin infusion will be started to attain a stable glucose level (4.0 -6.0 mmol/l) prior to commencement of the hyperinsulinaemic euglycaemia clamp (Time -120). A priming dose of a stable isotope tracer will be given directly into the cannula and stable isotope of glucose will be infused at -120 to +120 minutes to measure the rate of hepatic glucose production. At 0 minutes a low dose insulin infusion (0.3-0.5 mU/kg/min) will be commenced and a variable rate infusion of 20% dextrose "spiked" glucose tracer will be given to maintain the glucose level to 4.0-6.0 mmol/l. Blood samples of 4-13 mls each will be taken to measure glucose, insulin, c-peptide, glucagon, lipids and gut hormones at -120, -20, -15, -10, -5, 0, +30, +60, +90, +100, +110, +120, +150. At +120 minutes the insulin infusion and glucose tracer infusion will be stopped. At the same time points participants will be asked to complete appetite visual analogue scales. Participants will be fed and glucose infusion continued for a further 20 minutes to prevent hypoglycaemia. Depending on the patient's blood glucose control on arrival, the maximum duration of the whole visit will be up to 7 hours.

Blood samples will be centrifuged and the separated plasma kept in a - 20°C freezer. The isotopic enrichment of plasma glucose will be determined by gas chromatography mass spectrometry (GCMS) at the Wolfson Centre for Translational Research, Postgraduate Medical School, University of Surrey.

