3.1 Study outcome measures

Primary Endpoint

The primary outcome measure will be total energy intake and dietary composition in terms macronutrient proportions (fat, saturated fat, carbohydrates, sugars, fibre, protein and salt).

Secondary outcomes

The secondary outcome measures will be the ratings of hunger and satiety, gut hormones, bile acid and lipid levels before and after a standardised meal. In the clamp studies, the outcome will also be hepatic glucose output and insulin resistance.

4. Participant Entry

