Appendix

[figure not shown]
Table 1: Testing time points

Frequency test performed	Test
Preoperatively	400kcal standard meal plus venous blood sampling and visual analogue scores
Day 2	400kcal standard meal plus venous blood sampling and visual analogue scores
Day 7-30)	400kcal standard meal plus venous blood sampling and visual analogue scores
3 months	400kcal standard meal plus venous blood sampling and visual analogue scores
6-12 months	400kcal standard meal plus venous blood sampling and visual analogue scores

Table 2: Meal study protocol

Time	Intervention	Outcome measured	Outcome measured
0'	400kcal standard meal	Venous blood sampling 5ml	Visual analogue score
15'		Venous blood sampling 5ml	
30'		Venous blood sampling 5ml	
60'		Venous blood sampling 5ml	Visual analogue score
90'		Venous blood sampling 5ml	
120'		Venous blood sampling 5ml	Visual analogue score
150'		Venous blood sampling 5ml	
180'		Venous blood sampling 5ml	Visual analogue score

Diagrammatic representation of the metabolic study protocol

Metabolic study protocol

Time (min)	Action	Blood sampling (volume)			
		Glucose Conc and Enrichment (1ml)	Insulin (Serum) (3ml)	Glucagon (Serum) (2ml)	c-peptide/lipids/Gut hormones (Serum) (7ml)
- 120 to 0		Sliding scale insulin infusion 1 U/ml (0.1 - 6 ml/h) 15 minute interval blood glucose monitoring; maintenance of glucose at 4.0 – 6.0 mmol/l;			
-120		X	X		
-120 to +120		Start 6,6 ² H ₂ glucose infusion			
-20		X	X		
-15		X	X		
-10		X	X		
-5		X	X		
0		X	X	X	X
0-240		Low dose insulin infusion 0.3-0.5 mU/kg/min Initiation of variable infusion of 20% glucose spiked with 2H2 glucose; maintenance of clamp glucose at 4.0 – 6.0 mmol/l			
+30		X	X	X	X
+60		X	X		
+90		X	X	X	X
+100		X	X		
+110		X	X		
+120	Stop isotope and insulin Food will be given to the patient	X	X	X	X
+150		X	X	X	X
.

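### The clamp endpoint is a minimum glucose production rate with no window or averaging rule; a prespecified late-clamp mean is better defined and usually more precise

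*Combined protocol and SAP*

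**What the plan says.** Section 7 (Statistics and Data Analysis) states that for the metabolic study "the endpoint is the minimum endogenous glucose production rate". It adds that "we will have a power of 81% at a p level of <0.05 if 6 patients complete the study", a figure it bases on HOMA-IR results from one published study. Section 3.1 is less specific: "In the clamp studies, the outcome will also be hepatic glucose output and insulin resistance". It does not mention a minimum.

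Section 3 (Study Design) lists the blood samples after the start of the insulin infusion, in minutes and beginning at +30, as "30, +60, +90, +100, +110, +120, +150". The metabolic study table in the Appendix has a column headed "Glucose Conc and Enrichment (1ml)", marked at every one of these times. Section 3 also says: "At +120 minutes the insulin infusion and glucose tracer infusion will be stopped". The Appendix table repeats the stop at +120, but its row for the low-dose insulin infusion reads 0-240.

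Neither document section says which samples the minimum is taken over, whether the rates are smoothed, or what counts as steady state. No mean, SD or within-clamp variance for glucose production is given.

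**The concern.** The lowest of several noisy readings is an extreme value. Its expectation lies below the true suppressed rate, and the gap widens with the measurement noise and with the number of readings. On a plateau with normal error it also wastes information, because the readings it discards estimate the same quantity.

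Two things are at stake. The first is precision, in a substudy whose stated power rests on six completers. The second is comparability. Each patient is clamped up to four times under different dietary conditions. If one visit or group has noisier tracer data, or a missing sample, the endpoint moves without any change in physiology.

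The missing definition adds a third risk. An analyst could take the lowest of the four late samples or of all six on-insulin samples, or could include +150, and could make that choice after seeing the data.

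**Working it through.** **1. The plan's own figure.** The 81% cannot be reproduced, because the documents give no effect size, SD, sidedness or paired/unpaired design for the clamp. Solving backwards with the noncentral t distribution, 81% power at 0.05 two-sided needs a standardised effect of 1.45 for a paired test with n = 6, or 1.82 for 6 against 6.

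**2. Minimum against mean, on a plateau.** Let s be the SD of the error in one rate estimate. The late samples are +90, +100, +110 and +120 (k = 4). The +30 and +60 samples make k = 6. Simulation with normal error (1 million sets per case) gives:

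| k | Error correlation (AR(1)) | Bias of minimum | Variance of minimum | Variance of mean | Ratio |
|---|---|---|---|---|---|
| 3 | 0 | -0.85s | 0.559s² | 0.332s² | 1.68 |
| 4 | 0 | -1.03s | 0.492s² | 0.250s² | 1.97 |
| 4 | 0.5 | -0.82s | 0.668s² | 0.515s² | 1.30 |
| 4 | 0.8 | -0.55s | 0.844s² | 0.776s² | 1.09 |
| 6 | 0 | -1.27s | 0.416s² | 0.167s² | 2.49 |

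The k = 6 row assumes no trend from +30 onward.

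**3. When the bias cancels.** With k = 4, independent errors and the same s at both visits, the difference in bias is -1.03s + 1.03s = 0. If noise at one visit is q times that at the other, the leftover is -1.03(q - 1)s:
- q = 1.25 gives -0.26s.
- q = 1.5 gives -0.51s.

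If one visit loses one of its four samples, the leftover is 1.03s - 0.85s = 0.18s. The values of q are assumptions. Extra noise after treatment mimics a fall in production; extra noise at baseline or in controls hides one.

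**4. Power, under assumed variances.** Let R be the within-clamp error variance (s²) divided by the visit-to-visit variance. Assume a two-sided paired t-test with n = 6, and an effect of 1.454 SD that gives the mean of four samples exactly 81%. The SD of the change is inflated by

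r = √[(1 + R·V_min) / (1 + R·V_mean)],

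with V_min and V_mean the variances from step 2 in units of s². Power for the minimum is that of a t-test on 5 df with noncentrality 1.454·√6 / r = 3.56 / r. For R = 1 with independent errors, r = √(1.492/1.250) = 1.092 and power is 74%.

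| R | Correlation 0 | 0.5 | 0.8 |
|---|---|---|---|
| 0.25 | 79% | 80% | 80% |
| 0.5 | 77% | 79% | 80% |
| 1 | 74% | 77% | 80% |
| 2 | 70% | 76% | 79% |
| 4 | 65% | 74% | 79% |
| 8 | 61% | 73% | 78% |

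The smallest loss is 0.5 points (R = 0.25, correlation 0.8) and the largest is 81 - 61 = 20 points. If all variation were independent within-clamp error, power would be 53%, which is a limit and not a realistic case. Nothing in the documents selects a row or column.

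**5. Proportional error.** With lognormal error and k = 4, true rate set to 1, the SDs of the minimum and the mean are 0.146 and 0.150 at a CV of 30%, and 0.189 and 0.250 at 50%. The absolute SD of the minimum is then no larger. Relative to its own expected value, it is still 1.35 and 1.30 times as variable.

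**6. If production is still falling.** For a constant fall of b per sample, the four-sample mean lies 1.5b above the last true value. At b = 1s that is 1.5s above, while the expected minimum is 0.23s below. The variances are 0.25s² and 0.716s². The mean stays more precise, but it estimates the average over the window and not the final level.

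**The case against.** The strongest reply is that the plan never defines the minimum. It may be shorthand for the suppressed rate at the end of the clamp, already averaged, in which case there is no extreme-value problem. That is possible, but the text does not say so, and the only rule it states is a minimum.

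Several further points stand and limit the finding:

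- **Twice the error variance.** A reader might infer this as a general fact. It holds only for four independent normal errors on a plateau. Neighbouring clamp samples may well be correlated, and at correlation 0.8 the penalty nearly vanishes.
- **A definite loss of power.** A reader might infer that the plan's 81% is really 70% or 61%. The documents do not support that. The 81% comes from HOMA-IR and not from glucose production, no variance is given, and the t-test in Section 7 is described as between two groups, not as paired.
- **A false treatment benefit.** The sampling schedule is the same at each visit, so with equal noise and complete samples the bias cancels. When it does not cancel, it can act in either direction.
- **The purpose of the late samples.** A reader might infer that they were scheduled to be averaged. The protocol gives no reason for their spacing.
- **The late mean is not right under every reading.** It departs from the final suppressed rate if no plateau is reached by +90.

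It is also fair that this is a secondary outcome in a substudy, and that the HOMA-IR basis of the power statement is arguably the larger weakness in the same paragraph.

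**Conclusion.** The point holds in a limited form. As written, the endpoint is undefined in its window and averaging. On its literal reading it is biased low and, under normal error on a plateau, less precise than the mean of the same samples (variance ratio about 2.0, 1.3 and 1.1 at error correlations of 0, 0.5 and 0.8 for four samples). The bias threatens comparisons only where noise or usable sample count differs between visits or groups.

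The cost in power is not known: from under 1 point to about 20 under the assumed variances, paired design and normal error shown above. The case for change does not depend on that figure. A better-defined alternative exists at almost no cost, because enrichment is already measured at all four late times.

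**What to change.** In Section 7, replace the endpoint with: *the endpoint is the mean endogenous glucose production rate over the +90, +100, +110 and +120 minute samples*. Add that the slope over this window will be reported as a steady-state check. Use the same definition in Section 3.1.

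Reconcile the 0-240 insulin infusion row in the Appendix table with the stop at +120 in Section 3 and in the same table. The proposed window lies inside the infusion on either statement. Until they agree, however, it is unclear whether the window is the end of the clamp and whether +150 is an on-insulin sample.

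The cost is two sentences, with no extra blood, visits or patients. The downside to state openly is that if production is still falling between +90 and +120, the mean will lie above the final suppressed level; the reported slope will show when this happens.
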